16.1.2.2. Analysis of the Secondary Endpoints

The secondary endpoints are defined in [Table 6](#). The population for the analysis will be subjects in the ITT population with a baseline and at least 1 postbaseline value. For all continuous endpoints, an MMRM model will be used to analyze change from baseline to Week 12 visit using the fixed effects of treatment, visit, treatment-by-visit interaction, baseline, baseline-by-visit interaction, and region. Sensitivity analyses based on different missing mechanism will also be performed (imputation methods are defined in the SAP).

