2. STUDY DESIGN

2.1 Study Overview

This is a Phase 2, randomized, double-blind, placebo-controlled, parallel-group study to evaluate the safety, tolerability, and efficacy of BIIB104 in subjects with CIAS. Approximately 219 male and female subjects with stable schizophrenia from age 18 to 55 years, inclusive, will be recruited. Dosing with BIIB104 0.15 mg BID and 0.5 mg BID versus placebo BID will be evaluated over a treatment phase of 12 weeks. The study will be conducted at approximately 80 sites globally including non-English speaking countries.

The study includes a screening phase, a placebo lead-in phase, a randomized treatment phase, and a safety follow-up (SFU) phase to begin after the last dose of study treatment.

Screening evaluation will occur up to 35 days prior to randomization. Once eligibility has been established, a 7-day Placebo Lead-In evaluation will be conducted to assess the subject's ability to comply with dosing requirements. After Sponsor confirmation of eligibility and completion of baseline measurements at the Baseline/Day 1 Visit, subjects will be randomized in a 1:1:1 ratio to receive BIIB104 0.5 mg, BIIB104 0.15 mg, or placebo. Subjects will be dosed at approximately 12-hour intervals for 12 weeks. Total duration of subject participation will be approximately 19 weeks from screening to final follow-up visit.

[figure not shown]
There are 3 treatment groups and subjects are randomized in a 1:1:1 ratio into 1 of 3 treatment groups. The randomization will be stratified by region.

Table1: Treatment groups

Treatment Groups	Description
Placebo group	Up to 73 subjects to receive oral dosing BID with placebo for 12 weeks.
BIIB104 0.15 mg group	Up to 73 subjects to receive oral dosing BID with BIIB104 0.15 mg for 12 weeks
BIIB104 0.5 mg group	Up to 73 subjects to receive oral dosing BID with BIIB104 0.5 mg for 12 weeks

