3. SAMPLE SIZE JUSTIFICATION

The protocol states that:

Fifty-one subjects per treatment group will have approximately 80% power to detect a true mean difference of 3.5 in change from baseline MCCB Working Memory Domain score to Week 12 between the treatment and placebo groups. With the assumed drop-out rate of 30%, 73 subjects are required from each group to maintain the 80% power. This power calculation is based on a 2-

sided *t*-test assuming equal variance with a final significance level of 0.1, and a standard deviation of 7. The statistical software EAST 6.3® is used for sample size calculation. The sample size may be re-estimated based on blinded data review and evolving development of the study.

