4.3.2 Demographics and Baseline Characteristics

The demographic information of age, gender, ethnicity, race, height, weight, smoking status, and body mass index (BMI) will be summarized by treatment group. By-subject listings of such information will be provided.

The categorization of regions is determined from geography, language and culture from each country. The region category will be used as a covariate in statistical models and in subgroup analyses as appropriate.

Baseline clinical assessment variables include baseline MCCB domains, MCCB overall composite score, MCCB neurocognitive composite score, UPSA-Bi, SCoRS, PANSS total score, PANSS Positive Scale, PANSS Negative Scale, PANSS General Psychopathology Scale, SARA, C-SSRS, and CGI-S. Number of years since first episode of schizophrenia, age of first treatment of schizophrenia, number of previous episodes or exacerbations of schizophrenia in the last 24 months, and number of past psychiatric hospitalizations will also be summarized.

Medical history will be coded using the latest version of the Medical Dictionary for Regulatory Activities (MedDRA). The number (%) of subjects with history (including both ongoing and not ongoing medical conditions) will be summarized by system organ class and preferred term. A listing of medical history will be generated.

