The change from baseline will be summarized by treatment group at each post-baseline visit. A mixed model repeated measures (MMRM) model will be used as the primary analysis to analyze change from baseline of the endpoint of interest, using fixed effects of treatment group, study visit, study visit-by-treatment interaction, baseline value of the endpoint, and baseline-by-visit interaction. Region (stratification factor for randomization) will be included as a fixed effect but may be omitted in the case that the model fails to converge. An unstructured covariance matrix will be used to model the within-patient variance-covariance errors. If the unstructured covariance matrix results in a lack of convergence, the following structures will be used in order: heterogeneous Toeplitz (TOEPH), heterogeneous compound symmetry (CSH), antedependence (ANTE1), heterogeneous autoregressive (ARH1), autoregressive (AR1) and compound symmetry (CS). The first covariance structure yielding convergence will be used. If a structured covariance is used, the empirical “sandwich” estimator of the standard error (SE) of the fixed effects parameters will be used to deal with possible model misspecification of the covariance matrix. The Kenward-Roger approximation will be used to estimate the denominator degrees of freedom. The primary treatment comparison is BIIB104 treatment group versus placebo at the end of Week 12. In the primary analysis, missing data are assumed to be missing at random (MAR) [Rubin 1976]. To account for the interim analysis at the time of the final analysis, the median unbiased estimate of the primary treatment effect will be calculated as a supporting analysis.

However, for UPSA-Bi and SCoRS, which only have assessments at baseline and at Week 12, the primary analysis will be based on subjects who have both baseline and Week 12 assessments. An analysis of covariance (ANCOVA) model will be applied adjusting for treatment group and baseline value of the endpoint (UPSA-Bi or SCoRS, respectively).

Sensitivity analysis: Reference-based multiple imputation approach

The following sensitivity analysis will be performed to assess the robustness of the primary analysis with respect to deviation from the MAR assumption. All sensitivity analyses will be conducted for the ITT population.

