This is a supplementary analysis to assess the effect of individual treatment response in the ITT population only. The threshold, defined as the minimal clinically important difference (MCID), will be estimated based on the distribution-based approach and will use 1/2 pooled standard deviation at baseline calculated from subjects in the ITT population. A subject will be classified as a responder if their change from baseline (in terms of improvement) is greater or equal to the threshold, otherwise they will be classified as a non-responder. All subjects with missing data at Week 12 will be classified as non-responders.

The number of responders and non-responders will be modelled using a logistic regression with treatment group and baseline included as covariates. Region will also be included but may be omitted in the case the model fails to converge.

Visit windows for mapping efficacy endpoints

For efficacy data that are summarized by visit, data collected on all scheduled visits and all unscheduled visits will be mapped to an appropriate analysis visit using the windowing scheme shown in the following few tables. If there are 2 or more assessments available in the same analysis window for a subject, the assessment closest to the target visit day will be used for analysis. If there are 2 or more assessments in the same analysis window with the same distance from the target visit day, the later assessment will be used.

Table 2: Visit Windows for Efficacy Endpoints: MCCB, [REDACTED], and PANSS

Analysis visit	Target visit day	Analysis visit window
Baseline	1	Prior to the time of, or within one day after, the first treatment dose
Week 2	15	[2, 28]
Week 6	43	[29, 70]
Week 12	85	[71, 91]

* If subject terminate the treatment before Day 71, their visits will be mapped to corresponding analysis visit based on the analysis day (ADY).

Table 3: Visit Windows for efficacy endpoints: UPSA-Bi, SCoRS, [REDACTED]

Analysis visit	Target visit day	Analysis visit window
Baseline	1	Prior to the time of, or within one day after, the first treatment dose
Week 12	85	[71, 91]
Early Termination	N/A	[2, 70]

* If subject terminate the treatment early before Day 71, their visits will be mapped to nominal visit of “early termination”.

Table 4: Visit Windows for Efficacy Endpoints: CGI-S/CGI-I

Analysis visit	Target visit day	Analysis visit window
Baseline	1	Prior to the time of, or within one day after, the first treatment dose
Week 6	43	[2, 70]
Week 12	85	[71, 91]

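### The ANCOVA for UPSA-Bi and SCoRS leaves out region, the only stratification factor, with no reason given and contrary to the protocol model

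*SAP*

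**What the plan says.** Both documents name region as the stratification factor and name no other. SAP section 2.1 reads: "The randomization will be stratified by region".

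Protocol section 16.1.2.2 gives one model for all continuous secondary endpoints, an MMRM "using the fixed effects of treatment, visit, treatment-by-visit interaction, baseline, baseline-by-visit interaction, and region".

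SAP section 4.4.1 follows this for endpoints with several post-baseline visits: "Region (stratification factor for randomization) will be included as a fixed effect", to be dropped only if the model does not converge. It then makes an exception "for UPSA-Bi and SCoRS, which only have assessments at baseline and at Week 12". For these two endpoints the analysis set is subjects with both assessments, and the model is: "An analysis of covariance (ANCOVA) model will be applied adjusting for treatment group and baseline value of the endpoint". Table 5 in SAP section 4.4.3 says only that the method is ANCOVA and lists no terms.

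The responder logistic regression, which SAP section 4.4.3 also applies to UPSA-Bi and SCoRS, does carry the term: "Region will also be included but may be omitted in the case the model fails to converge". SAP section 4.3.2 adds a general statement: "The region category will be used as a covariate in statistical models and in subgroup analyses as appropriate".

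**The concern.** Reducing an MMRM to an ANCOVA is the natural step when there is one post-baseline visit, and the SAP explains it. That step removes visit and its interactions. It gives no ground for removing region, and no other ground is offered.

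Two things follow. First, the protocol and SAP specify different models for two key secondary endpoints, and SAP section 4.3.2 can be read as putting region back. Which model gives the reported estimate should be settled before unblinding. Second, stratified randomization balances the arms by region, so any regional differences in outcome contribute little to the true variance of the treatment contrast. A model without region still counts those differences as residual noise. Its standard error is then larger than it should be, the test is conservative, and some of the benefit of stratifying is lost.

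**Working it through.** **1. Side by side.** Write the protocol model as treatment + visit + treatment×visit + baseline + baseline×visit + region. With Week 12 as the only post-baseline visit, every visit term drops out or merges with its main effect, leaving treatment + baseline + region. The SAP has treatment + baseline. The difference is exactly one term.

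**2. The plan's own figures.** These concern the primary endpoint but set the analysed sample. With a difference of 3.5, SD 7 and two-sided alpha 0.10, noncentral-t power is 79.9% at 50 per group and 80.6% at 51, so the stated 51 reproduces. For dropout, 51/0.70 = 72.9, rounded up to 73 per group, and 3 × 73 = 219, which agrees with "With the assumed drop-out rate of 30%, 73 subjects are required from each group to maintain the 80% power". Expected completers are 219 × 0.70 ≈ 153. No power or SD is stated for UPSA-Bi or SCoRS.

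**3. Assumptions.** Let R² be the share of the variance remaining after baseline adjustment that region explains. The documents give neither R² nor the number of regions, so R² is taken as 0, 5, 10 and 20%. Dropout is d = 0.30, completely at random. Allocation is balanced within region at randomization.

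**4. Formulas.** Take the residual variance without region as 1.

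- Model variance without region is proportional to 1, and with region to 1 − R². The ratio of standard errors is 1/√(1 − R²).
- Dropout undoes part of the regional balance, so the true variance of the estimate without region is proportional to 1 − R² + dR².
- The model standard error without region therefore exceeds the true one by k = 1/√(1 − R² + dR²), and the two-sided size is 2[1 − Φ(1.645k)].
- If the model with region has 80% power, its standardized effect is 1.645 + 0.842 = 2.486. Power without region is Φ{[2.486 − 1.645/√(1 − R²)] / √[(1 − R² + dR²)/(1 − R²)]}.

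At R² = 20%: the SE ratio is 1/√0.80 = 1.118; k = 1/√0.86 = 1.078, giving size 0.076; power is Φ[(2.486 − 1.839)/1.037] = Φ(0.624) = 73.4%.

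| Assumed R² | SE ratio, without/with region | k | Size at nominal 0.10 | Power without region (80% with) |
|---|---|---|---|---|
| 0% | 1.000 | 1.000 | 0.100 | 80.0% |
| 5% | 1.026 | 1.018 | 0.094 | 78.6% |
| 10% | 1.054 | 1.037 | 0.088 | 77.0% |
| 20% | 1.118 | 1.078 | 0.076 | 73.4% |

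**5. Simulation check.** 219 subjects, 1:1:1 in permuted blocks of 6 within region (block size assumed), 30% random dropout, 12,000 runs per setting. Three region structures were assumed: three regions at 50/30/20%, three equal regions, and five regions at 40/25/15/10/10%. Ranges are across the three structures.

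| Assumed R² | SE ratio | Size without region | Power lost by omitting region (points) |
|---|---|---|---|
| 0% | 0.995–0.998 | 0.099–0.104 | −0.4 to −0.1 |
| 5% | 1.022–1.024 | 0.093–0.096 | 1.0 to 1.4 |
| 10% | 1.050–1.052 | 0.087–0.094 | 2.8 to 3.2 |
| 20% | 1.114–1.117 | 0.075–0.077 | 6.4 to 6.6 |

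Size with region lay between 0.093 and 0.105 in all settings. With no dropout the formula gives lower sizes without region (0.092, 0.083 and 0.066 at 5, 10 and 20%), because regional balance is then fully kept. The direction is the same.

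**The case against.** The strongest reply is that this is a matter of wording with little at stake. SAP section 4.3.2 already says region is to be a covariate, the ANCOVA sentence does not say that its two terms are the only ones, and the endpoints are secondary, in a Phase 2 trial without multiplicity adjustment or planned power for them. No source supports an R² of 10 or 20%. Baseline may absorb much of any stable regional difference, and at 5% the loss is only 1.0 to 1.4 points. Region-adjusted results for both endpoints are also planned elsewhere: in the responder model and, read literally, in the complementary analysis, which reuses the primary MMRM. Finally, the multiple-imputation models in section 4.4.1 do not list region either, so its absence is not confined to the ANCOVA.

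Much of this stands as a limit on size. The loss may be nil, and the larger figures rest wholly on assumption. It does not remove the discrepancy. The statement in section 4.3.2 is qualified and does not place region in a sentence that lists the model's adjustments without it. That leaves two readings for the main analysis of two key secondary endpoints. Convergence cannot be the reason either: the SAP states no such exception for the ANCOVA, and least squares is not iterative. The point about the imputation models is correct and bears on the fix.

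**Conclusion.** The concern holds. The SAP omits the sole stratification factor from the main model for UPSA-Bi and SCoRS, departs there from protocol section 16.1.2.2 and from its own MMRM and logistic models, and gives no reason. It should be corrected before unblinding.

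The consequence is a conservative test and some lost precision. Over an assumed R² of 0 to 20% with 30% random dropout, the standard error is about 0 to 12% larger than with region, size falls from 0.10 to about 0.08, and the power loss runs from none to about 6 points against an 80% reference that the documents do not claim for these endpoints. Where R² lies in that range cannot be determined from the documents. Type I error is not inflated, no bias arises under the random dropout assumed, and the primary endpoint is unaffected because its MMRM includes region.

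**What to change.** In SAP section 4.4.1, specify the UPSA-Bi and SCoRS model as *ANCOVA with treatment group, baseline value of the endpoint and region (randomization stratum) as fixed effects*, and repeat the terms in Table 5. Fit the same model to each imputed dataset in the reference-based sensitivity analysis of these endpoints. State as well whether region enters the imputation models, so that imputation and analysis are consistent. If region was left out on purpose, give the reason and record it as a change from protocol section 16.1.2.2.

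The cost is one model term and one sentence. The degrees of freedom spent equal the number of regions less one, a number the documents do not give. Where region explained nothing, simulated power with and without it differed by no more than 0.4 points, including with five regions.

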9.6. Randomization

Subjects will be randomized after all screening assessments and placebo lead-in have been completed and after the Investigator and the Sponsor have verified that the subjects are eligible per criteria in Sections 8.1 and 8.2.

Randomization will be performed using IRT. Randomization will be stratified by region. Subjects will be randomized in a 1:1:1 ratio to receive one of the following:

- BIIB104 0.15 mg
- BIIB104 0.5 mg
- placebo

Refer to the Study Reference Manual for additional details on randomization.

CONFIDENTIAL

The information contained herein may not be used, disclosed, or published without the written consent of Biogen MA Inc.

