Intermittent (non-monotonic) missing data will be imputed based on the MAR assumption and with a multiple imputation model using Markov chain Monte Carlo (MCMC) method within each treatment group. The imputation models will include baseline value and the values at each post-baseline week for the endpoint of interest. The MCMC method in the PROC MI procedure in SAS will be used with a single chain, with a burn-in of 1000, and a thinning of 100 and non-informative priors for all parameters.

Reference-based multiple imputation (MI) approach will be used to impute missingness post treatment discontinuation and consider a missing not at random (MNAR) mechanism for monotonic missing data. Imputed values in the reference group (placebo) will assume MAR. Imputed values in the BIIB104 treatment groups will be based on data from the placebo group using sequential regression MI model. Each sequential regression model (i.e., for imputation of values at a given week) will include visits of endpoint. This approach assumes no sustained benefit of BIIB104 after discontinuation of study treatment and limits post-discontinuation effects to that of placebo.

Two hundred imputations will be performed and from each of the imputed datasets, least square (LS) mean differences from placebo and their standard errors will be combined using Rubin's method [Rubin 1987]. PROC MIANALYZE procedure is used to produce a pooled LS mean estimate of treatment difference at Week 12, its 95% CI, and a pooled p-value.

Complementary Analysis: include data after intercurrent events

This is a complementary analysis to the primary and sensitivity analyses (efficacy estimand) for the ITT population. All observed data including those collected after intercurrent events [ICH E9 (R1) Addendum 2017], i.e. premature discontinuation of the study treatment, will be included. The estimate of this analysis reflects the treatment effect of BIIB104 seen as actually taken. This is considered [*de facto*] effectiveness estimand. When all data after intercurrent events are included, the same MMRM model as the primary analysis will be applied. In this complementary analysis, missing data are assumed to be missing at random [Rubin 1976].

The per-protocol analysis will be done using the same model as the primary analysis and applying in the per-protocol population.

Responder Analysis: threshold determined using distribution-based method

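### The imputation models for the reference-based sensitivity analysis omit region, so the estimate can be biased if regional drop-out differs between arms

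*SAP*

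**What the plan says.** Protocol 9.6: "Randomization will be stratified by region", with 1:1:1 allocation. For the primary MMRM, SAP 4.4.1 says: "Region (stratification factor for randomization) will be included as a fixed effect but may be omitted", the exception being non-convergence. SAP 4.3.2 forms regions from geography, language and culture and foresees region as a covariate in the statistical models.

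The sensitivity analysis in SAP 4.4.1 has two imputation steps:

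- Intermittent gaps are imputed under MAR, "using Markov chain Monte Carlo (MCMC) method within each treatment group". On content: "The imputation models will include baseline value and the values at each post-baseline week for the endpoint of interest".
- Data missing after discontinuation are imputed by sequential regression, with the active arms drawing on placebo data. Each of these models "will include visits of endpoint".

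Region appears in neither list. The SAP then pools LS mean differences over 200 imputations, but it does not state the model fitted to each completed data set. For UPSA-Bi and SCoRS the analysis model itself has no region term: "An analysis of covariance (ANCOVA) model will be applied adjusting for treatment group and baseline value of the endpoint".

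**The concern.** The MMRM assumes that data are missing at random given region, among other things; the imputation as written does not condition on region. The purpose of the analysis is to show what happens when the MAR assumption is relaxed after discontinuation. If a covariate disappears at the same time, a gap between the primary and sensitivity results mixes two causes: the intended reference-based assumption and the loss of region.

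It is plausible here that region matters. The endpoint is a cognitive test given in several languages, including in non-English-speaking countries (SAP 2.1). Drop-out could also differ by region and arm together. Only Japanese sites have extra post-dose safety checks on Days 1 and 8 and a Day 8 review of whether the subject may continue (Protocol Table 4 footnote 10 and section 14.3). Findings caused by the drug would arise more often in the active arms.

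**Working it through.** **The plan's own figures.** Protocol 16.6 and SAP 3 use a difference of 3.5, SD 7, two-sided alpha 0.10 and 30% drop-out. A t-test with 51 per group has 80.6% power. 51/0.70 = 72.9, rounded up to 73, and 3 × 73 = 219. These reproduce. The design standard error is 7 × √(2/51) = 1.39. The documents give no figure for the sensitivity analysis, no drop-out by region or arm, no regional effect and no number of regions, so everything below rests on assumed values.

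**Which step matters.** MCCB is analysed at Weeks 2, 6 and 12 (SAP Table 2). A missing Week 12 value has no later visit, so it is not an intermittent gap. The sequential regression therefore determines the imputed Week 12 values; the MCMC step acts on them only through Weeks 2 and 6.

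**When the error cancels.** Let w_r be the share of region r, d_Ar and d_Pr its drop-out on active and placebo, and e_r the error in the imputed mean when region is left out. Both arms are imputed from the placebo model, so e_r is roughly common to them, and

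bias ≈ Σ w_r (d_Ar − d_Pr) e_r.

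If drop-out by region is the same in both arms, every term is zero, however much drop-out varies between regions.

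**Size by hand, two equal regions.** Let δ be the regional difference in change that baseline and earlier visits do not predict, so e_1 − e_2 = δ. If active drop-out is x lower than placebo in region 1 and x higher in region 2, the absolute bias is 0.5 × x × δ.

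- Active 20/40%, placebo 30/30%: x = 0.10, bias 0.05δ. For δ = 2 to 4 this is 0.10 to 0.20.
- Active 15/45%, placebo 45/15%: x = 0.30, bias 0.15δ, which is 0.30 to 0.60.

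These are ceilings for a 2 to 4 point regional effect, because earlier visits usually carry part of it.

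**Simulation, two equal regions** (no true effect, SD 10, visit correlation 0.6, early, gradual or late onset of a 2 to 4 point regional effect). Absolute bias is 0.08 to 0.20 for the first pattern and 0.22 to 0.58 for the second. With region included it is at most about 0.02. With 20/40% in both arms it is about 0.01 to 0.02, with or without region.

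**Simulation, three regions** (shares 50/30/20%, baseline SD 10, correlation 0.6, monotone drop-out, 150,000 per arm, Week 12 ANCOVA on treatment, baseline and region). Entries are the estimate without region minus the estimate with region, for a spread of 2 to 7 points between extreme regions; Monte Carlo error is about 0.02 to 0.03.

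| Drop-out by region | True effect 3.5 | True effect 0 |
|---|---|---|
| A: 30% everywhere | −0.00 to +0.02 | −0.01 to +0.01 |
| B: 15/35/60%, both arms | −0.02 to +0.02 | −0.03 to +0.01 |
| C: placebo 10/20/40%, active 25/45/70% | −0.04 to −0.18 | −0.03 to −0.23 |
| D: placebo 45/20/10%, active 15/35/60% | −0.13 to −0.80 | −0.15 to −0.81 |

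The extremes in C and D need a 7-point spread, one full design SD. With spreads of 2 to 3.5 points, C gives 0.03 to 0.10 and D gives 0.13 to 0.41 in absolute size.

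**How the two causes mix.** With a true effect of 3.5 and a late 3.5-point spread, reference-based imputation with region gives 2.74 under D. That fall is what the analysis is designed to show. Without region it gives 2.33, and the further 0.4 is an artefact.

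**The case against.** A reader might infer that the estimate is biased whenever drop-out differs by region. The documents do not support that: randomization is stratified by region, so an error common to the arms cancels, as pattern B shows. A reader might also suppose that missing values are drawn around a single all-region mean. They are drawn given the subject's own values, so a regional difference in level that is already visible at baseline is largely carried along. Both limits stand and are built into the point.

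Other objections also hold in part:

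- The model fitted to each imputed data set is not stated, so the mismatch with the analysis is inferred from the primary MMRM. For UPSA-Bi and SCoRS there is no such mismatch, because their ANCOVA has no region term.
- It would be too strong to say that baseline is left out of the sequential models. SAP Table 2 lists baseline as an analysis visit, so the wording plausibly includes it.
- This is the only analysis that SAP Table 5 labels MNAR, but not the only one that departs from MAR. The responder analysis counts missing Week 12 values as non-response and includes region.
- Nothing in the documents gives a reason to expect mirror-image drop-out, so the larger figures mark an unfavourable case rather than a forecast.
- Region may be hard to estimate within an arm of at most 73 subjects, and the SAP already allows it to be dropped from the MMRM on non-convergence.

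None of this explains why a factor used for randomization and in the primary model should be absent from the imputation lists.

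**Conclusion.** The point holds in conditional form. Neither imputation model includes region, and the reference-based estimate for the MMRM endpoints can be biased if two things are true together: region predicts change beyond baseline and earlier visits, and regional drop-out differs between arms. The direction depends on which regions each arm loses.

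For a 2 to 4 point regional effect, the bias is about 0.1 to 0.2 points under moderate between-arm differences (0.2/3.5 = 6% of the target, 0.2/1.39 = 0.14 design standard errors) and about 0.2 to 0.6 under opposite patterns (0.6/3.5 = 17%, 0.6/1.39 = 0.43). Adding region removes it. The regional rates, effects, correlation and SD of 10 are assumptions, and a treatment effect that varies by region was not examined. The primary analysis is untouched. This is a worthwhile but optional improvement.

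**What to change.** In SAP 4.4.1, state that:

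- each sequential regression model includes baseline, region and all earlier visits of the endpoint;
- the MCMC model adds region to the variables already listed;
- for the MMRM endpoints, each imputed data set is analysed with baseline and region as covariates, as in the primary MMRM;
- if region is too sparse to estimate within an arm, it may be omitted under the non-convergence rule already given for the MMRM, or regions are pooled in a way fixed before unblinding. The pooling would have to be written out, since the MMRM section contains no pooling rule to refer to.

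The cost is a few sentences and an added term in the imputation code. The one small drawback is sparse region categories in the within-arm MCMC step, which the last item covers. Data collection, the estimand and the primary analysis do not change.
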